7.5.2.1.1 Primary Efficacy Endpoint: Upper Extremity Composite Score

Muscle strength based on the MVIC against a dynamometer will be measured bilaterally in the following upper extremity muscle groups: gross grip, shoulder abductors, elbow flexors, and elbow extensors. The UEC is derived from the sum of the average of the right and left total force values (measured in kg) for each muscle group. The comparison of the two treatment groups will be based on the change from baseline in mean UEC score between SA-ER and placebo using generalized estimating equation (GEE) repeated measures with baseline as a covariate.

Additional UEC-related parameters will serve as tertiary efficacy endpoints. The percent predicted total force values will be determined based on reference equations adjusting for age, gender, height, and weight. The percent predicted force will be calculated for each side and the bilateral percent predicted values will be averaged for each upper extremity muscle group (gross grip, shoulder abductors, elbow flexors, and elbow extensors). The mean of the four averages in percent predicted scores will be calculated to create a percent predicted UEC score, and analyzed relative to baseline to create a UEC mean change in percent predicted score. The change in mean percent predicted UEC score between SA-ER and placebo will be compared using the GEE repeated measures analysis.

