#### 4.4 Tertiary Efficacy Endpoints

- Upper Extremity Composite Percent Predicted: The percent predicted total force values will be determined based on reference equations adjusting for age, gender, height, and weight. The percent predicted force will be calculated for each side and the bilateral percent predicted values will be averaged for each upper extremity muscle group. The mean of the four averages in percent predicted scores will be calculated for each subject to create a percent predicted UEC score, and analyzed relative to baseline to create a UEC mean change in percent predicted score.
- Lower Extremity Composite Percent Predicted: The percent predicted total force values will be determined based on reference equations adjusting for age, gender, height, and weight. The percent predicted force will be calculated for each side and the bilateral percent predicted values will be averaged for each lower extremity muscle group. The mean of the five averages in percent predicted scores will be calculated for each subject to create a percent predicted LEC score, and analyzed relative to baseline to create a LEC mean change in percent predicted score.
- Muscle strength (Total Force in kg)) for Each Individual Muscle Group: Bilateral total force for each individual muscle group included in the UEC and LEC will be reported.
- Percent Predicted in Each Individual Muscle Group: Bilateral total force for each individual muscle group included in the UEC and LEC.
- Percent of Predicted Muscle Strength in Each Individual Muscle Group: Bilateral percent predicted total force for each individual muscle group included in the UEC and LEC.
- Percent Predicted in knee extensors: Bilateral percent predicted total force of knee extensors.
- Total Score on the GNEM-FAS
- Self-Care Domain Score on the GNEM-FAS
- Individual Neuromuscular Quality of Life Questionnaire: A 45-item self-report questionnaire with 4 domains on the impact of key muscle disease symptoms on the ability to perform basic activities of daily living, functional independence, relationships and overall well-being will be administered. The individual domain scores will be calculated.
- Clinical Global Impression Scale: Investigator assessment of severity of subject's GNEM using the CGI-improvement scale (CGI-I) during treatment, in 3 target areas.
- Creatine Kinase Levels: CK levels in serum will be measured to assess the degree of reduction of CK levels observed as a surrogate for muscle injury.

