### 5.3 Muscle Strength

The highest value of the three measurements collected for each muscle will be used for all HHD endpoints.

- **HHD Individual Muscle Strength Average Score** is calculated as the average of the right and left raw measurements in kg for an individual muscle group: individual muscle strength raw score = (left-side measurement + right-side measurement) / 2. If a value from the right or left side of an individual muscle group is missing, the missing value will be imputed using the non-missing value from the other side.
- **HHD Upper Extremity (UE) Composite Score** is calculated as the sum of the individual muscle strength average scores for the following muscle groups: gross grip, shoulder abductors, elbow flexors and elbow extensors. If a component individual muscle strength raw score is missing, the composite score will not be computed.
- **HHD Lower Extremity (LE) Composite Score** is calculated as the sum of the individual muscle strength average scores for the following muscle groups: hip flexors, hip extensors, hip abductors, hip adductors and knee flexors. Knee extensors will not be included in the calculation of the LE HHD composite score. If a component individual muscle strength raw score is missing, the composite score will not be computed.
- **HHD Total Composite Score** is calculated as the sum of the HHD UE composite score and the HHD LE composite score. If the UE or LE composite scores are missing, the HHD Total Composite Score will not be computed.
- **Predicted Normal HHD Values** will be derived for the raw right/left strength values from bilateral pinch, gross grip, shoulder abductors, elbow flexors, elbow extensors, hip flexors, hip extensors, hip abductors, hip adductors, knee flexors and knee extensors collected at Baseline using the regression equations outlined in Appendix 10.4. Predicted normal HHD scores for derived variables such as individual muscle raw score, UE/LE composite score, and total composite score will use the same computation method for raw

scores as described above but replace the observed values with the predicted normal HHD values.

- **% of Predicted Normal HHD Values** for the individual muscle groups and composite scores will be calculated as follows: (Observed Value / Predicted Normal HHD Value) \*100%. Baseline predicted normal values will be used to derive % of predicted normal values for all post-baseline study time points.

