- **% of predicted Total HHD UE and LE values** will be calculated as follows: (Raw strength value/Predicted normal strength value) \*100%. Percent predicted total normal strength value is the sum of percent predicted values of individual muscle groups.

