### 8.8.3 Analyses of Tertiary Endpoints

Analyses of the tertiary efficacy endpoints will follow the same methods as the primary analysis of the primary endpoint unless otherwise stated. No sensitivity analysis will be performed for tertiary efficacy endpoints.

Tertiary efficacy endpoints include the following:

- Upper Extremity Composite and Lower Extremity Composite Percent Predicted: The percent predicted total force values will be determined based on reference equations adjusting for age, gender, height, and weight (APPENDIX 10.2). The percent predicted force will be calculated for each side and the bilateral percent predicted values will be

averaged for each upper extremity muscle group. The mean of the four averages in percent predicted scores will be calculated to create a percent predicted UEC score for each subject, and analyzed relative to baseline to create a UEC mean change in percent predicted score. Similar methodology will be used to determine the percent predicted total force values for the LEC. Summary statistics on the changes from baseline will only be presented.

- Muscle Strength Total Force (kg) and Percent Predicted in Each Individual Muscle Group: Bilateral total force and percent predicted total force for each individual muscle group included in the UEC and LEC and percent predicted for the knee extensors will be reported. Summary statistics on the changes from baseline will only be presented.
- Total Score on the GNEM-FAS
- Self-Care Domain Score on the GNEM-FAS
- Individual Neuromuscular Quality of Life Questionnaire: The individual domain scores, a 45-item self-report questionnaire on the impact of key muscle disease symptoms on the ability to perform basic activities of daily living, functional independence, relationships and overall well-being will be recorded.
- Clinical Global Impression Scale: Investigator assessment of severity of subject's GNEM using the CGI-Severity scale (CGI-S) and improvement (CGI-I) during treatment. Physicians caring for each subject will provide a global assessment of change using a seven point scale ranging from 1 (normal) to 7 (extremely affected) for CGI-S at Baseline and -3 (severe worsening) to +3 (significant improvement) for CGI-I at Week 24 and Week 48. Descriptive statistics and number and percentage of subjects will be reported for CGI-S. The CGI-I score will be analyzed using GEE as well as a shift table conditional on the CGI-S categories at baseline.

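### The SAP defines percent-predicted UEC and LEC in two conflicting ways (mean of group percentages, ratio of composites), and one sentence in 5.3 that sums percentages is wrong as written

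*SAP*

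**What the plan says.** **Mean of percentages.** SAP 4.4 starts at the level of the side: "The percent predicted force will be calculated for each side and the bilateral percent predicted values will be averaged for each upper extremity muscle group". It then combines the groups: "The mean of the four averages in percent predicted scores will be calculated for each subject to create a percent predicted UEC score". The LEC entry does the same with five groups. SAP 8.8.3 repeats the rule ("The mean of the four averages in percent predicted scores will be calculated to create a percent predicted UEC score for each subject"), and so does Protocol 7.5.2.1.1 ("The mean of the four averages in percent predicted scores will be calculated to create a percent predicted UEC score"). Protocol 7.5.2.1.2 gives the five-group version for the LEC.

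**Ratio of composites.** SAP 5.3 says that percent of predicted normal "for the individual muscle groups and composite scores will be calculated as follows: (Observed Value / Predicted Normal HHD Value", times 100. Composite scores are named there explicitly. Appendix 10.3 builds the matching denominator by summing the groups' predicted normal values, each being the average of left and right.

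**Sum of percentages.** The last bullet of SAP 5.3, on total UE and LE values, first gives raw strength over predicted strength. It then states: "Percent predicted total normal strength value is the sum of percent predicted values of individual muscle groups".

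**Analysis.** For percent-predicted UEC and LEC, and for the individual muscle groups, SAP 8.8.3 says "Summary statistics on the changes from baseline will only be presented". Appendix 10.7 lists a GEE model for the same endpoints. Protocol 7.6.4.3 also specifies GEE.

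SAP section 1 ranks the SAP above the protocol on analysis methods. Nothing ranks one section of the SAP above another.

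**The concern.** A mean of percentages gives every muscle group equal weight. A ratio of sums weights each group by its predicted force, so grip counts most in the UEC. The two rules give different baselines and different changes for the same dynamometry readings. A programmer working from the derivation text (5.3 and 10.3) would build a different variable from one working from the endpoint text (4.4 and 8.8.3), and the precedence rule cannot settle a conflict inside the SAP.

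The literal sum in 5.3 is not a percentage of normal: a person at exactly 100% in all four upper-extremity groups would score 400.

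The plan also leaves open whether these endpoints get a model and a p-value or a descriptive table only.

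**Working it through.** The documents state no value for either score, so there is no figure to reproduce. The check applies each rule to one set of readings.

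**Formulas.** K groups (4 for UEC, 5 for LEC); observed o and predicted p, with a bar for the left-right average.
- Mean: 100 × (1/K) × Σ over groups of [(o_L/p_L + o_R/p_R)/2]
- Ratio: 100 × Σ ō / Σ p̄
- Sum: K × Mean, exactly

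**Inputs.** Assumed patient, not in the documents: man of 35, 80 kg, 1.75 m, with both sides at 45% (grip), 60% (shoulder abductors), 75% (elbow flexors) and 70% (elbow extensors) of predicted. Predicted values come from SAP Appendix 10.4. Weight is 80 × 9.80665 = 784.5 N; weight/height² is 26.12.
- Grip, male 30–39 median: 105 lb × 0.45359 = 47.627 kg
- Shoulder abduction: (165.16 − 0.910×35 + 0.126×784.5)/9.80665 = 23.67 and (178.90 − 1.128×35 + 0.134×784.5)/9.80665 = 24.94; average 24.305 kg
- Elbow flexion: right −4.55 + 11.24 + 1.83 + 22.78 = 31.30; left −3.85 + 10.63 + 1.31 + 19.66 = 27.75; average 29.522 kg
- Elbow extension: right −2.80 + 8.33 + 4.18 + 12.37 = 22.08; left −2.45 + 8.18 + 4.44 + 11.32 = 21.49; average 21.785 kg
- Predicted UEC: 123.24 kg

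**Baseline.**
- Mean: (45 + 60 + 75 + 70)/4 = 62.5%
- Ratio: (21.432 + 14.583 + 22.142 + 15.250)/123.24 = 73.407/123.24 = 59.6%
- Sum: 250

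**Weights.** The mean gives each group 25%. The ratio gives grip 47.627/123.24 = 38.6%, shoulder abductors 19.7%, elbow flexors 24.0% and elbow extensors 17.7%.

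**A 2 kg UEC gain.** Placed in one group, it moves the mean by 100 × 2/(4 × p̄) = 50/p̄. The ratio moves by 200/123.24 = 1.62 wherever the gain falls.

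| Where the 2 kg falls | Mean | Ratio |
|---|---|---|
| Grip | +1.05 | +1.62 |
| Shoulder abductors | +2.06 | +1.62 |
| Elbow flexors | +1.69 | +1.62 |
| Elbow extensors | +2.30 | +1.62 |
| 0.5 kg in each group | +1.77 | +1.62 |

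The table divides by the group averages; keeping the sides separate changes no entry by as much as 0.01 point.

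**Sign reversal.** Grip +3 kg with elbow extensors −2 kg:
- Mean: 25 × (3/47.627 − 2/21.785) = −0.72
- Ratio: 100 × (3 − 2)/123.24 = +0.81

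**Dependence on the profile.** Two other assumed patients, at 40/60/70/80% in the same group order:
- Man of 40, 75 kg, 1.75 m: baseline 62.5% against 57.9%; the same offsetting change gives −0.82 against +0.82.
- Woman of 40, 60 kg, 1.63 m: 62.5% against 58.0%; −1.35 against +1.38.

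For the LEC in that man, with hip flexors, hip extensors, hip abductors, hip adductors and knee flexors assumed at 10/30/50/20/30%, the mean is 28.0% and the ratio 25.6%. The two rules coincide at a visit when every group is at the same percentage of predicted.

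**The case against.** Wherever the documents define the percent-predicted UEC as an endpoint (protocol synopsis, Protocol 7.5.2.1.1, SAP 4.4 and 8.8.3), they use the mean. Section 5.3 and the appendices read like a general derivation list: they carry items that are not endpoints here, such as a total composite, bilateral pinch and gait speed. An analyst who starts from 8.8.3 would compute the mean. This supports the mean as the intended rule, but it does not remove the conflict: 5.3 applies the ratio to composite scores by name, and no sentence says that 4.4 and 8.8.3 prevail.

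The sum sentence is probably a slip. It follows a ratio and seems to explain the denominator, so a sum of predicted values may have been meant, which would be the ratio again. That is plausible, but the sentence as written still needs correcting.

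The example puts the whole gain in one muscle to show the widest gap. That is fair: for an evenly spread 2 kg gain the gap is only 1.77 − 1.62 = 0.15 points.

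Two stronger readings are tempting. A reader might infer three rival formulas with three different treatment effects. The sum is exactly 4 or 5 times the mean, with the same weighting, test statistic and p-value, so there are two weightings and one faulty sentence. A reader might also infer that the sponsor means to choose the formula once the data are seen. Nothing in the documents indicates this; the endpoint text points consistently to the mean.

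**Conclusion.** The conflict between the mean (SAP 4.4, 8.8.3 and the protocol) and the ratio (SAP 5.3, Appendix 10.3) is real and unresolved, and the sum sentence in 5.3 is wrong as written. In the assumed patients the UEC baselines differ by 2.9 to 4.6 percentage points (62.5 − 59.6 and 62.5 − 57.9). Changes differ by an amount that depends on which muscles change: small for an even change, and opposite in sign for some offsetting ones. These sizes rest on assumed patients; the difference in weighting follows from the formulas themselves.

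The consequence is limited. These are tertiary endpoints without multiplicity control. The primary UEC and the key secondary LEC and knee extensor endpoints are in kg and do not use percent predicted, and GNEM-FAS mobility does not either. No confirmatory conclusion turns on this point. The disagreement between 8.8.3 and 10.7 about modelling is a separate inconsistency in the same endpoints, of the same low weight. This is a clean-up worth making, not a threat to the trial's main result.

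**What to change.** - Keep one definition of percent-predicted UEC and LEC: percent predicted per side, averaged over the two sides, then averaged over the four or five groups, as in SAP 4.4 and 8.8.3.
- In SAP 5.3 and Appendix 10.3, remove the observed-over-predicted ratio for composite scores, and delete the sum sentence in the last bullet of 5.3.
- Use the same side-level-then-average rule for individual muscle groups in 5.3 and 10.3. At present those sections divide the group's observed average by its predicted average, which can differ when the two sides have different predicted values and different percentages. Removing only the composite ratio would leave that mismatch.
- Make 8.8.3 and Appendix 10.7 agree on whether these endpoints are modelled by GEE or only summarised. If they are only summarised, record the departure from Protocol 7.6.4.3 and exempt them from the nominal testing statement at the end of 8.8.3.

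The cost is SAP wording only: no new data, no change in sample size and no effect on the primary or key secondary analyses. It should be done before unblinding.

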#### 5.4 Patient Reported Outcomes

- **GNEM Functional Activities Scale (GNEM-FAS) Total Score** will be calculated as the sum of the Total Scores range from 0 to 100 with higher scores representing greater independence with functional activities. Subscale scores will be calculated for the Mobility, Upper Extremity and Self-Care domains. Mobility subscale scores range from 0 to 40 with higher scores representing greater mobility. Upper Extremity subscale scores range from 0 to 32 with higher scores representing more skilled, independent use of the arms during functional activity performance. Self-Care subscale scores range from 0 to 28 with higher scores representing greater independence with functional care activities.
- **Individual Neuromuscular Quality of Life Scale (INQoL) Subscale and QoL:** The individual domain scores will be calculated using the scoring algorithms outlined in Appendix 10.5 Derived Variables.
- **Number of doses administered** will be calculated for each subject by summing the number of doses administered over all visits.
- **Prior medications** include all medications taken by the subject from 30 days prior to the signing of the informed consent until the first dose of study medication is administered.
- **Concomitant medications** include all medications that are taken after the first dose of study medication is administered.

## 6 ANALYSIS POPULATIONS

### 6.1 Primary Analysis Set

The Primary Analysis Set will include all randomized subjects with a baseline measurement and at least one post-baseline measurement. Each subject will be included in the treatment group assigned at randomization, regardless of the treatment received. This set will be used for the primary analyses of all efficacy endpoints.

### 6.2 Per Protocol Set

The per protocol analysis set consists of all subjects in the Primary Analysis Set who have a dosing compliance rate  $\geq 80\%$ .

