7.4.6 Prior and Concomitant Therapy

7.4.6.1 Prohibited Medications

Patients may not be enrolled if they have a history of more than 30 days treatment with SA in the past year, used any investigational product or investigational medical device within 30 days prior to Screening, or if they require any investigational agent prior to completion of all scheduled study assessments. Ingestion of ManNAc, SA or related metabolites; IVIG; or anything that can be metabolized to produce SA in the body is prohibited during the 60 days

prior to Screening and throughout the study. If ManNAc, SA or another substrate was used more than 60 days prior to Screening, the time period of use, the compound used, and the dose and dose regimen should be recorded. If a patient has been on substrate replacement therapy in the past, the investigator must consider the potential confounding effects of this therapy before enrolling the patient as a subject in the study.

IT IS ESSENTIAL THAT THE SUBJECT COMMIT TO NOT INGESTING ManNAc OR SIMILAR OTHER SA-PRODUCING COMPOUNDS DURING THE CONDUCT OF THIS STUDY AS IT COULD CONFOUND THE INTERPRETATION OF THE RESULTS. THE STUDY WILL ANALYZE URINE FOR THE PRESENCE OF ManNAc TO DETECT NONCOMPLIANCE WITH THIS ESSENTIAL REQUIREMENT.

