### 5.2 Drug Compliance

Compliance = total dosage received / total dosage planned \* 100%. Total dose planned is calculated for the period a subject is on investigational product, which is either 48 weeks if a subject completes the study, or the period up to early withdrawal.

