## 8 STATISTICAL METHODS OF ANALYSIS

### 8.1 General Principles

Efficacy analyses will be based on the primary analysis set. GEE analysis ([Hanley et al. 2003](#)) for repeated measures will be performed to compare the two treatment groups with respect to the changes from baseline of primary endpoint, secondary endpoints, and all tertiary efficacy endpoints, using an exchangeable working covariance structure among time points. Baseline, gender and region will be included as covariates in the model. Compound symmetry may be used if convergence is not achieved or if the AIC is larger than the one from the exchangeable covariance structure.

In general, randomly missing efficacy data for an individual subject will be treated as missing. The GEE method might not adequately cover the projected decline for these subjects and may not be appropriately conservative. In such cases a single imputation method will be used to estimate the change in strength over the remaining time of the study as described in [Section 7.1](#) and these imputed values will be used for the GEE analysis. This method of imputation will be the primary analysis method for all repeated measures endpoints.

A sensitivity analysis without use of the single imputation method for dropouts will be also be performed using the same GEE model.

The statistical analyses will be reported using summary tables, figures, and data listings. Statistical tests will be 2-sided at the alpha =0.05 significance level. All analyses and tabulations will be performed using SAS®. Continuous variables will be summarized with means, standard deviations, standard errors, medians, minimums, and maximums. Categorical variables will be summarized by counts and by percentages of subjects in corresponding categories.

The final analysis will be conducted at Week 48.

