## 8.7 Primary Efficacy Endpoint and Analysis

The primary clinical efficacy analysis will be the changes from baseline in UEC score over time for the SA-ER group compared with placebo based on bilateral strength recorded in the following muscle groups using a dynamometer: gross grip, shoulder abductors, elbow flexors, and elbow extensors. The UEC is derived from the sum of the muscle groups. Each muscle group value will represent the average of the right and left total values (measured in kg).

The comparison of the two treatment groups will be based on the changes from baseline over time in mean UEC score between SA-ER and placebo using the week 48 ls-means from GEE repeated measures analysis with baseline, gender, and region as covariates. Region is considered as a covariate to account for the heterogeneity of the disease observed in some European countries and Israel relative to North American patients.

The imputations method described in Section 7.1 will be used to estimate the change in strength for dropouts. Sensitivity analyses will also be performed as described in Section 8.1.

In addition, the primary analysis will be repeated in the Per Protocol population.

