#### 8.8.4 Analyses of Sialic Acid, Creatine Kinase and Free ManNAc

The following clinical lab outcomes will be analyzed using GEE using the SA analysis set. No imputation will be performed for missing data. Free, total, and bound urine SA and urine ManNAc are collected at Baseline, Week 24, and Week 48. All other labs are collected every 8 weeks up to Week 48.

- Free SA: Free SA levels in serum assess the drug concentration in the bloodstream resulting from treatment and are the best indicator of compliance with the treatment regimen. Free SA levels in serum are expressed in micrograms of SA per ml of serum
- Free SA in urine: Free SA levels in urine will be assessed to determine the overall absorption of SA-ER over time. Free SA levels in urine will be expressed in micrograms of SA per ml of urine.

- Total SA in urine: Total SA levels in urine will be assessed to determine the accumulated excretion of sialic acid from dosing. Total SA levels in urine will be expressed in micrograms of SA per ml of urine.
- Bound Sialic Acid in urine: Bound SA levels in urine is calculated as the difference between each subject's total sialic acid and free sialic acid in urine corrected for total protein. Bound sialic acid in urine may also be corrected for creatine and calculated as the difference between each subject's total sialic acid and free sialic acid corrected for creatine. The primary correction for SA will be total protein with creatine correction only used when an alternate method is required
- Creatine Kinase Levels: CK levels in serum will be measured to assess the degree of reduction of CK levels observed as a surrogate for muscle injury.
- Free ManNAc in urine: Free ManNAc levels in urine will be assessed to determine the amount of naturally occurring ManNAc in the urine of study subjects and the stability of these levels over time. Free ManNAc levels in urine will be expressed in micrograms of SA per ml of urine. Changes from baseline in Free ManNAc levels in urine will be analyzed.
- Free ManNAc/Free SA in urine: The ratio of free ManNAc to free SA levels in urine will be assessed to ensure compliance with the restriction placed on ManNAc consumption during the study period.

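### No planned efficacy analysis excludes subjects with prohibited sialic-acid intake, because the Per Protocol Set is filtered on study-drug compliance alone

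*SAP*

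**What the plan says.** **The restriction.** Protocol 7.4.6.1 prohibits ManNAc, SA, related metabolites, IVIG and anything metabolized to SA, from 60 days before Screening to the end of the study. It adds: "IT IS ESSENTIAL THAT THE SUBJECT COMMIT TO NOT INGESTING ManNAc OR SIMILAR OTHER SA-PRODUCING COMPOUNDS DURING THE CONDUCT OF THIS STUDY", because intake could confound the results. Protocol 7.5.4 schedules a urine ManNAc test at Screening, Baseline and Weeks 16, 32 and 48 (or Early Termination) to find breaches.

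**The analysis sets.**
- SAP 6.1: the Primary Analysis Set is as randomized, "regardless of the treatment received".
- SAP 6.2: "The per protocol analysis set consists of all subjects in the Primary Analysis Set who have a dosing compliance rate" of at least 80%.
- SAP 5.2: "Compliance = total dosage received / total dosage planned", with the planned amount counted over 48 weeks "or the period up to early withdrawal". It measures study tablets only.
- Protocol 7.6.3 defines no Per Protocol Set, so SAP 6.2 is the only definition.

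**Where the sets are used.** SAP 8.7 says that "the primary analysis will be repeated in the Per Protocol population", and SAP 8.8.1 does the same for the three key secondary endpoints. The other planned check is in SAP 8.1: "A sensitivity analysis without use of the single imputation method for dropouts will be also be performed using the same GEE model".

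**The detection analysis.** SAP 8.8.4 says: "The ratio of free ManNAc to free SA levels in urine will be assessed to ensure compliance with the restriction placed on ManNAc consumption". It also analyses urine free ManNAc on its own. Both are analysed by GEE, with no limit for a positive result and no link to an analysis set.

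**The concern.** A Per Protocol analysis is normally where a trial asks what happens among subjects who kept to the rules that matter for the comparison. Here the protocol names one such rule as essential and collects data to police it, but the Per Protocol definition ignores it. A placebo subject who takes every placebo tablet and also takes ManNAc counts as per protocol.

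At stake is how a small or null UEC difference would be read. If some placebo subjects took a sialic-acid source, the difference could shrink, and neither the primary analysis nor its Per Protocol repeat could separate that from a lack of drug effect.

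A second, smaller issue is the ratio used as the compliance check. Its denominator is urine free SA, which SAP 8.8.4 itself treats as a marker of SA-ER absorption. In the SA-ER arm the ratio therefore reflects study drug as well as illicit ManNAc.

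**Working it through.** **1. Does any planned efficacy analysis remove these subjects?**
- Primary Analysis Set (SAP 6.1): as randomized, with baseline and at least one later value. No.
- Analysis without dropout imputation (SAP 8.1): same subjects, different handling of missing values. No.
- Per Protocol Set (SAP 6.2): tablet compliance only. No.
- Removal for a protocol deviation (Protocol 7.3.3): optional, and it does not take out data already collected. No.

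**2. The plan's own figure.** SAP 3.7 gives about 80 subjects, 1:1, a 5 kg difference, SD 6, two-sided alpha 0.05 and 90% power. With 40 per arm:
- standard error = 6 × √(2/40) = 1.342 kg
- power = Φ(5/1.342 − 1.96) = Φ(1.767) = 96.1% (95.7% by the t distribution)

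The stated 90% is not reproduced; it needs 32 per arm by the t distribution. Since 64/(1 − 0.20) = 80, a 20% dropout allowance would explain the gap, but none is stated. The gap is conservative and does not affect this point.

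**3. Size of possible dilution.** The documents give no rate, so c, the share of placebo subjects with prohibited intake, is an assumption. Each such subject is assumed to gain the full 5 kg, which is the worst case.
- Difference = 5 × (1 − c)
- Power if kept = Φ(5(1 − c)/1.342 − 1.96)
- Power if excluded, with m placebo subjects left = Φ(5/(6√(1/40 + 1/m)) − 1.96), assuming intake is unrelated to outcome

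| c | Difference if kept | Power if kept | m | Power if excluded |
|---|---|---|---|---|
| 0% | 5.00 kg | 96.1% | 40 | 96.1% |
| 5% | 4.75 kg | 94.3% | 38 | 95.7% |
| 10% | 4.50 kg | 91.8% | 36 | 95.2% |
| 20% | 4.00 kg | 84.6% | 32 | 94.0% |

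Power falls below the stated 90% by c = 15%, where it is 88.6%. These figures use all 40 subjects per arm; the tablet-compliance filter would lower the number in the real Per Protocol Set.

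**4. The ratio.** If SA-ER multiplies urine free SA by k and illicit intake multiplies urine ManNAc by m', the ratio changes by m'/k. The documents give no human urine figures, so the values are illustrative. With k = 3:
- compliant SA-ER subject: 1/3 = 0.33
- SA-ER subject with tripled ManNAc: 3/3 = 1.00, which looks like no change
- with no study-drug effect (k = 1), the same intake: 3/1 = 3.00

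**5. The specimens and weeks.** SAP 8.8.4 gives urine ManNAc at Baseline and Weeks 24 and 48; Protocol Table 2.1 and SAP 10.1 show Weeks 16, 32 and 48 after Baseline. Protocol Table 2.1 takes ManNAc from the urinalysis sample and urine SA from the first-morning void, while the SAP 10.1 footnote takes both from the first-morning void. Under the protocol, the ratio mixes two specimens.

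**The case against.** The strongest reply is that this affects little.

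- **The primary test is sound.** As-randomized inclusion is right for a superiority test. Intake in the placebo arm biases towards no difference and does not inflate type I error. This stands; only supportive analyses are affected.
- **Detection does not rest on the ratio.** Free ManNAc is analysed without SA in the denominator (SAP 4.6 and 8.8.4), serum free SA is taken at Baseline and each later clinic visit (Protocol 7.5.3), and SAP 8.9 lists concomitant medications by patient. This stands. But none of these has a limit or a rule that changes an analysis set. SAP 8.8.4 expects some naturally occurring ManNAc, so its mere presence cannot define a breach.
- **The ratio problem is not in the arm that matters most.** Study drug does not move the ratio in placebo subjects, whose intake would dilute the contrast. This stands, and it makes the ratio a secondary point.
- **The dilution is a worst case.** Protocol 7.4.3 describes 3 g/day as not efficacious, so occasional intake need not reproduce the full effect. Even at c = 10% the worst case leaves power above 90%. Equal dilution of the Per Protocol and primary results also assumes that intake is unrelated to tablet compliance. All of this stands.

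A reader might infer that every analysis is contaminated, and that the flawed ratio is the cause. The documents support neither. They report no intake, and the ratio feeds no analysis set, so a perfect ratio would leave SAP 6.2 unchanged. The cause is the missing exclusion rule.

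**Conclusion.** The point holds in a limited form. No planned efficacy analysis excludes subjects with prohibited intake, and the Per Protocol repeat of the primary and key secondary analyses cannot show whether such intake diluted the difference. This follows from the definitions and needs no assumption.

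The size does need assumptions. If 10% to 20% of placebo subjects had the full assumed effect, 5 kg would become 4.5 to 4.0 kg; the true loss could be anywhere from nil upwards, because no rate is given. The gain from excluding them assumes that intake is unrelated to outcome.

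The ratio is a poor check in the SA-ER arm by the SAP's own description of its denominator. How poor cannot be said without human urine data.

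This should be corrected before unblinding. It does not threaten the validity of the primary test.

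**What to change.** **SAP 6.2, before unblinding, identically for both arms.** Exclude from the Per Protocol Set any subject with:
- recorded post-baseline use of ManNAc, SA, IVIG or another SA-producing compound; or
- post-baseline urine free ManNAc, creatinine-corrected and not as the ratio, above a limit fixed on blinded data.

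The limit needs a rule that one extreme value cannot set, such as one built on the median and a robust spread of pooled Screening and Baseline values. The highest pre-dose value would not do, because one undeclared user could set it. It would also flag compliant subjects: with 80 × 2 = 160 pre-dose and 80 × 3 = 240 later values, treated as independent and exchangeable, about 240/161 = 1.5 would exceed it by chance. A common limit assumes that SA-ER does not itself shift urine ManNAc, which the documents do not address; the planned free ManNAc analysis can check this.

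**Reporting.** List exceedances by subject and count them by arm.

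**Serum free SA.** A check in placebo subjects could reveal direct SA use, which ManNAc testing would not identify. Report it as a separate supplementary analysis. As a Per Protocol criterion it would exclude from one arm only, after unblinding.

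**Reconcile** the ManNAc sampling weeks and specimen between SAP 8.8.4, SAP 10.1 and the protocol, and the ManNAc unit in SAP 8.8.4, which is worded as an amount of SA.

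**Cost.** SAP wording and a slightly smaller Per Protocol Set. The urine tests and medication records are already planned, and creatinine is already in the protocol's urinalysis panel.
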